3.2 Schedule of Events

Table 1 Schedule of Visits and Assessments

Study Procedure	Screen	Baseline Day 1	Week 1 Day 8	Week 2 Day 15	Week 4 Day 29/ET
Visit	1	2	3	4	5
Visit Window	-30 days	N/A	± 3 days	± 3 days	± 3 days
Parents/Caregivers informed consent	X				
Demographics	X				
Medical and surgical history	X				
Physical examination ^a	X	X			X
I/E criteria	X	X			
Hematology and Serum Chemistries ^b	X				
Vital signs, weight, height ^c	X	X	X	X	X
vIGA-AD ^d , EASI ^d , BSA ^d , SCORAD ^d	X	X	X	X	X
WI-NRS pruritus ^e	X	X	X	X	X
POEM ^f	X	X	X	X	X
Local Tolerability Assessments ^g		X	X	X	X
CDLQI ^h , IDQoL ^h , DFI ^h	X	X	X	X	X
Medical Photography ⁱ		X	X		X
Drug application and Parents/Caregivers training in clinic ^j		X	X	X	
Dispense/Redisperse investigational product kit ^k		X	X	X	X ^l
Weigh investigational product tubes ^l		X	X	X	X
Dispense/review diary	X	X	X	X	X
Compliance determination ^m			X	X	X
Adverse event assessment ⁿ	X	X	X	X	X
Concomitant medications	X	X	X	X	X
Study Exit ^o					X

	STATISTICAL ANALYSIS PLAN, Version 1.0
Protocol Number: ARQ-151-315	Sponsor: Arcutis Biotherapeutics, Inc.

Footnotes from above table:

- a. Limited physical examination: skin (including assessment of Fitzpatrick skin type at Screening only), lungs, and heart only.
- b. To be collected at Screening. In addition, laboratory safety tests may be performed at various unscheduled time points, if deemed necessary by the Investigator.
- c. Height will be collected at Screening and Week 4/Day 29. Weight should be obtained using a calibrated weight scale and the same scale should be used for a subject throughout the duration of the study. The subject should remove shoes and heavy clothing (sweaters or jackets), and empty pockets. The subject should stand with both feet in the center of the scale with their arms at their side and hold still. Record the weight to the nearest decimal fraction (for example, 25.1 kilograms). Measure the weight in triplicate and report the average weight in EDC. A 5% weight loss (whether or not intentional or other explained) should be reported to the medical monitor in a timely manner and before the next clinic visit.
- d. The vIGA-AD assessment will be a 5-point scale ranging from clear (0) to severe (4) and is evaluated for the entire body except the scalp, palms, and soles. EASI takes into account overall severity of erythema, infiltration/papulation, excoriation, and lichenification, in addition to extent of BSA affected. The 4 clinical signs will be graded on a 4-point scale (0 [absent] to 3 [severe]) for 4 body regions (head and neck, upper extremities, lower extremities, and trunk). Total EASI score will be calculated as a sum of scores of all 4 body regions. EASI total score will range from 0 (absent) to 72 (severe). Total BSA affected by AD will be determined for all body surfaces except the scalp, palms and soles. **The vIGA-AD assessment should be completed prior to other physician assessments.** SCORAD total score will range between 0 and 103.
- e. Parents/guardians/caregivers of children will report pruritus at home on a daily basis starting 7 days prior to the Baseline/Day 1 visit, and then every day thereafter using a diary. WI-NRS score will be determined by assessing worst itch over the past 24 hours. The scale is from 0 (no itch) to 10 (worst itch) and this value will be recorded each day. Caregiver/parents will be given instructions on how to complete this questionnaire.
- f. POEM will be completed for all subjects by proxy completion.
- g. Local tolerability assessments should be recorded prior to study drug application for the Investigator assessment of skin irritation (Berger and Bowman skin irritation score) and 10-15 minutes post-drug application for the Subject's '0-3' burning/stinging assessment. Parents/guardians will complete assessment for subjects. Subject's burning/stinging assessment at Week 4/Day 29 will be provided by a recall assessment of burning/stinging experienced post drug application on the previous day (Day 28). **Note for Investigator tolerability assessments: reactions at the site of product application, which may occur post-Baseline, should be differentiated from the preexisting inflammation associated with the subject's atopic dermatitis.** If a subject is entering ARQ-151-313 Open Label Extension study, then the Subject's '0-3' burning/stinging assessment will be performed as described in the ARQ-151-313 protocol for Baseline/Day 1.
- h. The CDLQI will be completed by parents/caregivers for subjects ≥ 4 years of age. The IDQoL will be completed by parents/caregivers for subjects < 4 years. The Dermatitis Family Impact Questionnaire (DFI) will be completed by parents/caregivers for all subjects.
- i. Photography of AD lesion(s) selected by the Investigator will be performed at all investigational sites. All efforts will be made to de-identify the subjects. Canfield equipment will be used to capture photographs. Subjects who are unwilling to participate in the medical photography will be allowed to opt out of this procedure, as documented on the Informed Consent Form.
- j. Subjects to apply assigned IP during clinic visits, except for the Day 29/ET visit. If a subject is entering ARQ-151-313 Open Label Extension study, then subjects will apply IP as described in the ARQ-151-313 protocol for Baseline/Day 1.
- k. It is expected that kits will be dispensed based on %BSA affected. See IP Handling Manual for details. On Day 8 and 15, dispensing of IP is optional. Site should review IP kit to ensure sufficient IP is available until the next visit and only dispense additional IP if needed. On Day 29, if the subject is unable to perform the Day 29 clinic visit due to COVID-19 restrictions (isolation, quarantine, etc.) then additional IP may need to be dispensed using Unscheduled Visits or home delivery of IP, so IP can continue to be applied at home until the subject is able to return to the clinic to complete the Day 29 assessments (contact sponsor representative for guidance).
- l. Every tube should be weighed and recorded when dispensed and returned. See IP Handling Manual for details.

 Innovaderm Research ■■■	STATISTICAL ANALYSIS PLAN, Version 1.0
Protocol Number: ARQ-151-315	Sponsor: Arcutis Biotherapeutics, Inc.

- m. Compliance determination is described in the IP Handling Manual.
- n. All AEs should be collected starting after the first application of the investigational product through the end of the study. All SAEs should be collected starting after the signing of informed consent through 30 days after the last day of the application of the investigational product or the end of the study (whichever is later). Any AEs (whether serious or non-serious) and clinically abnormal laboratory test value(s) will be evaluated by the Principal Investigator (PI) and treated and/or followed up for up to 30 days after end of treatment or until symptoms or value(s) return to normal, or acceptable level, as judged by the PI (if the subject is continuing into the ARQ-151-313 OLE study, then AEs from this study (ARQ-151-315) will only be followed until they exit from this study). Subjects who enroll into the open label extension study (ARQ-151-313) must complete the ARQ-151-315 Week 4/Day 29 visit as this visit (Week 4/Day 29) is the Day 1 visit for ARQ-151-313.

3.3 Treatment

Roflumilast cream 0.05% or vehicle cream will be administered QD for 28 days (+/- 3 days).

- Roflumilast cream 0.05%
- Vehicle cream

3.4 Randomization, Replacement, and Unblinding Procedures

Randomization will take place at the Baseline/Day 1 visit after the Investigator confirms that the subject meets all eligibility criteria. Subjects will be randomly assigned to apply ARQ-151 cream 0.05 % QD, or matching vehicle QD. Assignment of drug or vehicle will be made at a 2:1 ratio (drug:vehicle) and stratified by Baseline/Day 1 vIGA-AD score ('Mild' vs. 'Moderate'), and by study site according to a computer-generated randomization list. Kits containing tubes of study medication will be assigned to each subject using an Interactive Web Response System (IWRS). A subject may receive more than one kit for the treatment period. The kits and tubes are blinded, and each kit is numbered with a unique kit number.

Subjects that withdraw or are discontinued from the study will not be replaced.

The study is double-blinded, therefore neither the subjects nor the Investigator, sponsor and clinical personnel will be aware of which treatment an individual subject receives.

3.5 Changes to the Analysis from the Protocol

Not applicable

 Innovaderm Research ■■■	STATISTICAL ANALYSIS PLAN, Version 1.0
Protocol Number: ARQ-151-315	Sponsor: Arcutis Biotherapeutics, Inc.

4 POPULATIONS FOR ANALYSIS

4.1 Intent-to-Treat (ITT) Population

Intent-to-Treat population will include all subjects who are randomized, and all subjects will be analyzed according to the treatment group and stratum to which they were randomized.

4.2 Per Protocol (PP) Population

Per protocol population will include all subjects who are randomized, at least 80% compliant with study medication application have a vIGA-AD assessment within the Week 4 visit window, and show no “major deviations” from the study protocol that would affect the interpretation of efficacy. A complete list of major deviations from the study protocol will be created prior to unblinding and include a list of all subjects who will be excluded due to those major deviations. See section [7.2](#) for more details.

All subjects will be analyzed according to the actual treatment group they received and the randomized stratum. Actual and randomized treatment will only differ if the subject received the wrong treatment throughout their participation in the study.

4.3 vIGA-AD Moderate ITT Population

vIGA-AD Moderate ITT population will be a subset of the ITT population with vIGA-AD score (randomized score) ‘Moderate’ at randomization.

All subjects will be analyzed according to the treatment group and the stratum to which they were randomized.

4.4 WI-NRS Population

WI-NRS population will be a subset of the ITT population who:

1. Parent/caregiver completed at least 4 of 7 evaluable daily WI-NRS questionnaires during the last 7 days of the Screening period.
2. Have a mean baseline WI-NRS score ≥ 4.0 , defined as the average of all non-missing scores reported during the last 7 days of the Screening period if at least 4 of 7 evaluable daily WINRS questionnaires available. If 4 or more evaluable daily questionnaires are missing, then the baseline score will be treated as missing.

All subjects will be analyzed according to the treatment group and stratum to which they were randomized.

 Innovaderm Research ■■■	STATISTICAL ANALYSIS PLAN, Version 1.0
Protocol Number: ARQ-151-315	Sponsor: Arcutis Biotherapeutics, Inc.

4.5 Safety Population

Safety population will include all subjects who are enrolled and received at least one confirmed dose of study medication.

Subjects will be analyzed based on the treatment group received and the stratum they belong to. Actual and randomized treatment will only differ if the subject received the wrong treatment throughout their participation in the study.

5 GENERAL CONSIDERATIONS

Formats and layouts of tables, listings, and figures (TLF) will be provided in a separate document (output general layout is described in [Appendix 1](#)).

5.1 Sample Size

Approximately 650 subjects are planned to be randomized in this study. To test the secondary endpoint of IGA success in subjects with a vIGA-AD score of ‘Moderate’ at randomization, approximately 490 of the subjects to be accrued will have vIGA-AD score of ‘Moderate’ at randomization. Randomization will be stratified by vIGA-AD score (‘Mild’ vs. ‘Moderate’), and study site.

This study is designed to differentiate between a vehicle cream treatment that has an IGA success rate of 22% or less and ARQ-151 cream treatment with an IGA success rate of 37% or more. The hypothesis is that the IGA success rate among subjects treated with ARQ-151 cream 0.05% is significantly greater than the IGA success rate among subjects treated with vehicle cream.

This sample size provides more than 90% power to detect 15% difference between treatment groups on vIGA-AD success at Week 4 at $\alpha=0.025$ using a 2-sided stratified Cochran-Mantel-Haenszel (CMH) test. The results from a recent phase 2 study (ARQ-151-212) of ARQ-151 cream 0.05% compared to vehicle treatment were used to estimate the treatment difference. The vIGA-AD success rate at Week 4 was approximately 38% in the ARQ-151 cream 0.05% group compared to 22% in the vehicle. Similarly, approximately 37% of subjects demonstrated vIGA-AD success at Week 4 in the ARQ-151 cream 0.15% group. This sample size also provides more than 80% power to detect an overall 15% difference between treatment groups on IGA success at Week 4 in subjects with vIGA-AD score ‘moderate’ at randomization. The same testing method, the stratified CMH test, will be used as for the primary endpoint.

 Innovaderm Research	STATISTICAL ANALYSIS PLAN, Version 1.0
Protocol Number: ARQ-151-315	Sponsor: Arcutis Biotherapeutics, Inc.

5.2 Baseline

Unless otherwise specified, baseline value will be defined as the last non-missing assessment prior to or concurrently with the first study treatment application (including unscheduled/retest assessments). The randomization date will be used in place of the date of first treatment application for randomized subjects who discontinue without having treatment applied. If the last non-missing assessment is performed on the same date as the first study treatment administration and time is not available, it is assumed that the assessment took place prior to IP application, per study site training, and the assessment will be considered as baseline, except for adverse events (AEs) and medications starting on the first study treatment dose administration date which will be considered postbaseline.

Average weekly baseline WI-NRS is defined as the average of all non-missing scores reported during the last 7 days prior to treatment if at least 4 of 7 evaluable daily WI-NRS questionnaires available. Daily baseline WI-NRS is defined as the last non-missing assessment prior to or concurrently with the first study treatment dosing. Day 1 WI-NRS score will be used to calculate the value for week 1 only when it is collected after the application of the first study drug. If Day 1 WI-NRS score is collected prior to or concurrently with the application of the first study drug, then the Day 1 WI-NRS score will be included in baseline calculation.

For investigator/subject tolerability assessments, baseline is derived as the measurement taken on the day of first application of study drug.

5.3 Reference Start Date and Analysis Day

Analysis day will be calculated from the first study treatment administration date* and will be used to derive start/end day of assessments or events.

Analysis day = (Date of event – Date of first dose administration*) + 1 if date of event is on or after the date of first dose administration of study treatment*;
= (Date of event – Date of first dose administration*) if date of event is before the date of first dose administration of study treatment*.

In the situation where the assessment/event date is partial or missing, analysis day will be missing.

* For randomized subjects who discontinued study before the first application of study treatment, the date of randomization will be considered instead of the date of the first application of study treatment.

 Innovaderm Research ■■■	STATISTICAL ANALYSIS PLAN, Version 1.0
Protocol Number: ARQ-151-315	Sponsor: Arcutis Biotherapeutics, Inc.

5.4 Windowing Conventions

Visits will be analysed as scheduled. Unscheduled, early termination visits, and/or retest measurements will only be included if a scheduled measurement is not available and the early termination or unscheduled/retest measurement falls within the analysis visit windows as described in [Table 2](#), [Table 3](#), and [Table 4](#) when appropriate. Unscheduled/retest measurements will be listed.

If there is more than one assessment for a given timepoint and analysis visit when a scheduled measurement is not available, the assessment closest to the target day will be considered.

Table 2 Analysis Visit Windows for Efficacy Endpoints, Vital Signs and Local Tolerability Assessment

Analysis Visit	Target Day	Lower Limit	Upper Limit
Week 1	8	2	11
Week 2	15	12	22
Week 4	29	23	43

Table 3 Analysis Visit Windows for Clinical Laboratory and Physical Examination

Analysis Visit	Target Day	Lower Limit	Upper Limit
Week 4	29	23	43

Table 4 Windows for the derivation of Average Weekly WI-NRS

Days for calculation of weekly average	Week (Derived)
(-6, 1) *	Baseline
(2, 8)	Week 1
(9, 15)	Week 2
(16, 22)	Week 3
(23, 29)	Week 4

* If Day 1 WI-NRS score is collected prior to or concurrently with the application of the first study drug (randomization for randomized subjects who were never treated with study drug), then the Day 1 WI-NRS score will be included in baseline calculation.

Note: With the caveat described in footnote **, if more than one WI-NRS score is available on the same day, the worst score of the day will be considered in the analyses.

 Innovaderm Research ■■■	STATISTICAL ANALYSIS PLAN, Version 1.0
Protocol Number: ARQ-151-315	Sponsor: Arcutis Biotherapeutics, Inc.

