7.6. Unscheduled Visit

Unscheduled visits may be necessary to repeat testing following abnormal laboratory results, for follow-up of AEs, or for any other reason, as warranted in the judgement of the Investigator.

The following information will be collected for all subjects:

- Concomitant medications/procedures
- AEs

The following information also will be collected:

- vIGA-AD and EASI
- BSA affected with AD
- Local tolerability assessment (by Investigator)

However, if an unscheduled visit is required for reasons other than safety (e.g. procedures such as labs or images that were either missed at the regular subject visit or need to be repeated), the vIGA-AD and EASI, BSA affected with AD, and Local Tolerability assessment (by Investigator) are not required.

The rules for how to tally vIGA-AD, BSA or other proportions of categorical responses will be described in the Statistical Analysis Plan.

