7.8. Treatment Stopping Rules

If a subject has non-cutaneous adverse events of concern, clinically significant laboratory values or any condition that the investigator determines could possibly be related to the study drug, the Investigator should immediately contact the Medical Monitor to discuss if the subject should be discontinued from treatment with investigational product.

Treatment for any individual subject will be discontinued if the subject experiences:

- A serious adverse event (SAE) or a clinically significant non-serious AE which in the opinion of the Principal Investigator or Medical Monitor warrants discontinuation from the study for that subject's well-being.
- A treatment-emergent severe (Grade 3) laboratory abnormality (confirmed by repeat sample; see [Appendix 8](#) and the Laboratory Toxicity Grading section in the appendix for more information).

Parents/caregivers will be advised to promptly report any changes in behavior that could signal psychological distress or emotional distress.

Treatment should be interrupted:

- If a subject develops an application site reaction with the clinical appearance of an 'irritation reaction', and with a severity of a Dermal Response Score of 5 (erythema, edema and papules) or greater on the scale of Berger and Bowman, treatment should be interrupted for up to one week and may then be resumed if the reaction has, in the opinion of the Investigator, adequately resolved.

Treatment should be discontinued:

- If the application site reaction reoccurs, treatment should be discontinued permanently, and the subject followed until the reaction resolves.

For cases of suspected allergic contact dermatitis, the medical monitor and sponsor should be notified and there should be discussion about performing patch testing to further evaluate. Patch testing is encouraged in such cases.

In the event of a medical emergency where unblinding is required to provide medical care to the subject, refer to the most current IWRS User Manual ([Section 6.5](#)). Contact the Medical Monitor and the Sponsor promptly.

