5.8 Handling of Retests, Unscheduled Visits, and Early Termination Data

Retests measurements, Unscheduled measurements, and ET visit assessments will be included in analysis and be summarized via analysis visit windowing according to the windowing conventions in section 5.4.

All data from retest, unscheduled measurements and ET visit assessments will be listed.

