13.3 Vital Signs

Descriptive statistics will be presented for vital signs (systolic blood pressure, diastolic blood pressure, heart rate, body temperature, and weight). Observed values, change from baseline and percent change from baseline values will be presented by treatment group at each scheduled visit.

The number and percentage of subjects with gain or lose $\geq 5\%$ from baseline in body weight over the course of the study will be summarized. The BMI percentile rather than BMI kg/m^2 will be summarized using descriptive statistics (n, mean, standard deviation, median, Q1, Q3, minimum, and maximum) on observed values, change from baseline and percent change from baseline values.

A listing of all vital sign assessments including weight, BMI, and BMI percentile will be provided.

 Innovaderm Research ■■■	STATISTICAL ANALYSIS PLAN, Version 1.0
Protocol Number: ARQ-151-315	Sponsor: Arcutis Biotherapeutics, Inc.

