13.4 Local Tolerability Assessments

The investigator's assessment of the application site reaction will be summarized by visit using both categorical methods (number and percentage of subject with each score) as well as continuous methods (e.g., mean, standard deviation, etc.)

Local tolerability (burning/stinging sensation) assessed by the parent/caregiver for the subject will be summarized using number and percentage similarly.

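### By-visit tolerability and vital-sign tables leave out unscheduled and early-termination readings when a scheduled one shares the window, and no worst post-baseline tolerability summary is planned

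*SAP*

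**What the plan says.** **Selection rule.** SAP 5.4 analyses visits as scheduled. Unscheduled, ET and retest readings "will only be included if a scheduled measurement is not available and the early termination or unscheduled/retest measurement falls within the analysis visit windows". Table 2 is titled "Analysis Visit Windows for Efficacy Endpoints, Vital Signs and Local Tolerability Assessment" and sets Week 1 at Days 2-11, Week 2 at Days 12-22 and Week 4 at Days 23-43. Table 3, for laboratory tests and physical examination, has a Week 4 window only (Days 23-43).

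**Second statement of the rule.** SAP 5.8 says that retest, unscheduled and "ET visit assessments will be included in analysis and be summarized via analysis visit windowing according to the windowing conventions in section 5.4". It therefore defers to 5.4 and does not override it. It adds: "All data from retest, unscheduled measurements and ET visit assessments will be listed".

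**Safety summaries.** Under SAP 13.4 the investigator's "assessment of the application site reaction will be summarized by visit using both categorical methods" and continuous ones, and the caregiver's burning/stinging score is summarized in a similar way. No worst-value summary is mentioned. SAP 13.3 presents vital signs, including weight, at each scheduled visit. Separately, the number of children gaining or losing at least 5% "from baseline in body weight over the course of the study will be summarized". SAP Section 2 names both local tolerability and the incidence of this weight change as safety endpoints.

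**What is measured off schedule.** Protocol 7.6 collects the investigator's tolerability score at unscheduled visits, unless the visit is for a reason other than safety. Its list does not include weight, vital signs or burning/stinging. Protocol 7.5 gives the ET visit the content of the Week 4 visit, so all of these are measured there. Protocol 7.8 interrupts treatment for an irritation reaction "with a severity of a Dermal Response Score of 5 (erythema, edema and papules) or greater on the scale of Berger and Bowman".

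**The concern.** A scheduled-first rule suits efficacy, where every child should be compared at the same planned time. For local tolerability it works differently. Protocol 7.6 ties the off-schedule investigator score to safety visits, so it is the score most likely to record a reaction. The rule sets it aside whenever a planned visit in the same window produced a score.

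A reaction that meets the trial's own interruption threshold could then be missing from every tolerability table. A reader of those tables would take them as the graded record of a named safety endpoint in children aged 2 to 5 years and could not see that such scores had been removed by rule.

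**Working it through.** The plan states no figure on this point, so there is none to reproduce. The check sets the Table 2 windows against the visit ranges in the Schedule of Visits (target day ±3).

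**1. Are there gaps between windows?**

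| Visit | Target day | Protocol range | Table 2 window |
|---|---|---|---|
| Week 1 | 8 | 5-11 | 2-11 |
| Week 2 | 15 | 12-18 | 12-22 |
| Week 4 | 29 | 26-32 | 23-43 |

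The windows are contiguous: 10 + 11 + 21 = 42 days, which is every day from 2 to 43. Each protocol range lies inside its window.

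**2. A child with all three scheduled readings.** Every window already holds a scheduled value. An unscheduled investigator score on any of the 42 days is therefore left out of the by-visit table.

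**3. Worked case (hypothetical).** A child scores 0 at the Week 1 visit on Day 8 and 5 at an unscheduled safety visit on Day 10. Day 10 falls in 2-11, so Week 1 is tabulated as 0. Treatment is interrupted under Protocol 7.8. If the reaction has settled by the Week 2 visit, that visit's score does not show it either. The 5 then stands in no tolerability table.

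**4. ET visits.** An ET reading is left out when it falls after a completed scheduled visit but in the same window:

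- Week 1 visit on Day 5, 8 or 11: ET on Days 6-11, 9-11 or none is left out (6, 3 or 0 days).
- Week 2 visit on Day 12, 15 or 18: ET on Days 13-22, 16-22 or 19-22 is left out (10, 7 or 4 days).
- ET on Day 23 or later with no scheduled Week 4 visit is used as Week 4. ET in the Week 2 window with no scheduled Week 2 visit is used as Week 2.

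With visits on Days 8 and 15, the affected ET days are 3 + 7 = 10 of the 27 days from Day 2 to Day 28. Over the permitted visit days the range is 0 + 4 = 4 to 6 + 10 = 16 of 27. These are counts of calendar days, not of children or readings.

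**5. Which measures are exposed?**

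| Measure | Unscheduled safety visit | ET visit sharing a window |
|---|---|---|
| Investigator Dermal Response score | collected; left out of the by-visit table | left out |
| Burning/stinging | not on the Protocol 7.6 list | left out |
| Weight and vital signs, by visit | not on the Protocol 7.6 list | left out |
| Count with at least 5% weight change | data source not stated | data source not stated |

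**6. Physical examination.** Table 3 has no window before Day 23, so an earlier ET examination has no analysis visit to be assigned to.

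**The case against.** The strongest reply is that a by-visit table needs a rule that picks one value per child per visit, and 5.4 supplies one. Protocol 8.3.2 asks for the investigator's score by visit, and SAP 13.4 follows it. Nothing is contradicted, the rule is the same in both blinded arms, and safety has no formal testing. All set-aside readings are listed. A reaction severe enough to interrupt treatment would fit the adverse-event definition in Protocol 7.7.1, and SAP 13.1 tabulates application-site TEAEs without reference to visit windows.

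Much of this stands. It is a good reason to leave the by-visit tables as they are. It does not replace a worst-value summary. Neither Protocol 7.1.6 nor 7.8 requires a Dermal Response score of 5 or more to be recorded as an adverse event. Adverse events are graded on the CTCAE scale rather than that of Berger and Bowman, and a listing gives no comparison between arms. The SAP uses worst-case summaries elsewhere: maximum severity and strongest relationship for TEAEs, and the worst score when several itch scores fall on one day.

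Three stronger readings are tempting and are not supported:

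- *The weight-change count omits ET weights.* SAP 13.3 and Protocol 8.3.4 define it over the whole study, and SAP Section 2 defines it as change on study. No text limits it to windowed values. No text says that it uses all values either, and the general wording of 5.8 exempts nothing, so a programmer could read it both ways.
- *About 37% of ET data are lost* (10/27). That treats ET timing as uniform and visits as fixed on Days 8 and 15. It measures neither subjects nor bias.
- *The tables favour the active cream.* Unscheduled visits may be for any reason, and ET visits may follow a parent's decision or non-compliance. The documents give no basis for a difference between arms.

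**Conclusion.** The point holds for the by-visit local tolerability and vital-sign summaries. It is clearest for the investigator's Dermal Response score. In a child with all three scheduled scores, no unscheduled score can enter the table, whatever its value. For burning/stinging, vital signs and by-visit weight, the omission arises mainly through ET visits that share a window with a completed scheduled visit. For the count of at least 5% weight change there is an ambiguity to settle, not a demonstrated exclusion.

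The documents give no rate of unscheduled or ET visits, so neither the number of affected readings nor the size or direction of any effect on the arm comparison can be stated. The readings are missing from summary tables, not from reporting. No efficacy result or significance level is touched. The conclusion rests on reading 5.4 as written and on 5.8 deferring to it. It is a worthwhile, inexpensive improvement to the reporting of a named safety endpoint, not a flaw in the trial's inference.

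**What to change.** - **SAP 5.4:** keep the rule for efficacy and for the by-visit tables.
- **SAP 13.4:** add a worst post-baseline summary per arm using every assessment after the first dose (scheduled, unscheduled and ET). Give the maximum Dermal Response score, the number of children with a score of 5 or more, and the maximum burning/stinging score. State how the Day 1 burning/stinging score is treated: it is taken 10 to 15 minutes after the first application, but SAP 5.2 labels it baseline.
- **SAP 13.3:** state that the count of at least 5% weight gain or loss uses every post-baseline weight, including unscheduled and ET.
- **Optional, SAP 13.5:** add an ET/last-assessment row for physical examination, since Table 3 has nothing before Day 23.

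The cost is a few sentences and a few table rows. No new data are needed and no clinical rule changes. The one downside is that the worst-case tolerability figures may look slightly less favourable than the by-visit ones.
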